10.3 Planned Interim Analyses

Interim analyses will focus on the statistical testing of the primary endpoint with descriptive reporting of the secondary endpoints as well. Interim analyses will be conducted after enrollment of approximately: 25%, 50%, 75%, and 100% of participants are enrolled. This interval may be modified by the DSMB.

A Lan-DeMets spending function analog of the O'Brien-Fleming boundaries will be used for the outcome of COVID-19-free survival. The provided table assumes four interim analyses with the final analysis with an overall alpha=0.025. The boundaries are truncated at |Z| = 3.01.

Interim Analysis	Sample Size	Z	P-value
1	~875 (25%)	> 3.1	.0019
2	~1750 (50%)	> 3.1	.0036
3	~2625 (75%)	> 2.78	.0179
Final	3500 (100%)	> 2.30	.025

Should a stopping boundary be crossed, we would recommend an analysis to determine whether the findings are consistent across secondary endpoints, such that a clear answer is achieved. In the event of early halting due to efficacy, the study will immediately convert to an open-label observational cohort of hydroxychloroquine prescribed to all consented participants.

Based on the public health situation, the DSMB has the prerogative to alter the stopping rules.

Futility Analysis:

If the conditional power is <20% at the time of the second interim analysis with approximately 50% of participants enrolled, discontinuation should be considered as a possible recommendation by the DSMB. The sample size re-estimation will be considered here as well as the pace of enrollment.

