Secondary Endpoints	 Incidence of confirmed SARS-CoV-2 detection Incidence of possible COVID19 symptoms Incidence of all-cause study medicine discontinuation Ordinal Scale of COVID-19 Disease maximum severity if COVID-19 diagnosed Incidence of Hospitalization for COVID-19 or death Incidence of study medication-related side effects 	
Duration of Participation	• Recruitment and follow up will be internet-based. All patients will be followed for at least 4 weeks. Recruitment is expected to take 4 weeks, for a total study duration of 8 weeks. But the total study duration will depend on the actual rate of enrollment. Study drug will be given for a maximum of 12 weeks.	
Inclusion Criteria	 Healthcare worker, at high risk of COVID-19 exposure: Persons primarily working in emergency departments (physicians, nurses, ancillary staff, triage personnel) Persons primarily working in intensive care units (physicians, nurses, ancillary staff, respiratory therapists) Persons performing aerosol generating procedures: ex. Anesthesiologists, nurse anesthetists (CRNAs) First responders: ex. EMTs, paramedics 	
	 Age >=18 years of age Provision of Informed Consent 	
Exclusion Criteria	 Active COVID-19 disease Confirmed prior COVID-19 disease Current fever, cough, shortness of breath Contraindication or allergy to chloroquine or hydroxychloroquine Prior retinal eye disease Known Chronic Kidney disease, Stage 4 or 5 or dialysis. Known glucose-6 phosphate dehydrogenase (G-6-PD) deficiency. Weight <40 kg Current use of hydroxychloroquine or cardiac medicines of flecainide, amiodarone, digoxin, procainamide, or propafenone Current use of medications with known significant drug-drug interactions: artemether, lumefantrine, mefloquine, tamoxifen, or methotrexate. 	

Statistical	 10% transmission rate for high-risk healthcare workers with		
Assumptions	no treatment		
	 Alpha = 0.025 (to account for two treatment groups vs. placebo comparisons) Assuming 15% lost to follow up in the placebo group and 5% lost to follow up in each treatment group N=3500 has 80% power to detect a hazard ratio of 0.65, using a two-sided log-rank test 		

Schematic of Study Design:

At the close of the study, any participant with ongoing illness will continue to be assessed for up to a total of 90 days after the common closing date.

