4.1 DESIGN

Randomized, double-blind clinical trial, parallel design. This is an event-driven trial. Subjects will be followed until study termination. Study drug will be prescribed for up to 12 weeks.

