4.3.2 Randomization

- Participants will be randomized at the investigation pharmacy
- The investigational pharmacy will dispense masked study medicine (hydroxychloroquine or placebo)
- The study medicine will be shipped to participants to arrive ~1 day after enrollment
- 4.3.3 Day 1 Virtual visit
 - Verify receipt of study medicine
 - Clinical status check-in
 - Begins taking study medicine (2 tabs), then 2 tabs in 6-8 hours
 - Query for symptom status
 - Query for hospitalization or SAEs
- **4.3.4** Weekly Virtual visit
 - Clinical status check-in for COVID-19 symptoms
 - Assessment of adherence and side effects by self-report
 - Continue study medicine up to 12 weeks
 - Query for study medicine side effects since enrollment
 - Query for SARS-CoV-2 testing
 - Query for hospitalization or SAEs
- **4.3.5** Study termination virtual visit (to be completed on or shortly after the common closing date for the study)
 - Clinical status check-in for COVID-19 symptoms
 - Query for study medicine adherence and side effects since enrollment
 - Query for SARS-CoV-2 testing
 - Query for hospitalization or SAEs
 - Query for pregnancy status
 - Final outcome assessment
- **4.4** Individually identifiable health information: Name, date of birth, and phone number will be collected so as to prescribe study medication. Email addresses will be collected for communication. If participants are hospitalized, the hospitalization date will be collected.

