10.4 Final Analysis Plan

We will assessCOVID-19-free survival in high-risk healthcare workers who receive hydroxychloroquine compared to those who receive placebo.

We will compare survival in a time-to-event analysis for COVID-19-free survival using Log-rank test with survival displayed as a Kaplan-Meier curve. Analysis will be intention-to-treat. Persons who develop confirmed COVID-19 or die will be considered failures. Persons lost to follow up will be censored.

Secondary endpoints for incidence will be assessed via Fisher's Exact test for the proportions by study arm. The secondary endpoint on the ordinal scale will be assessed with a proportional odds model.

PREP COVID-19

Version 1.0 27 March 2020

Among those with symptoms, severity of symptoms (recorded on a 0-10 visual analog scale) will be compared via Mann-Whitney U by study arm.

A priori subgroup analyses will include assessment by:

- Days from Exposure
- Decile of age
- Sex as a biological variable
- Censored subjects, who became symptomatic before receipt of the first dose of study medicine, will be separately analyzed and reported.

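### Section 10.3 times log-rank looks by percent enrolled but prints fixed Z values built for percent of events: alpha exceeds 0.025, and the 50%-enrolled look holds only about 9% of events

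*Combined protocol and SAP*

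**What the plan says.** Section 10.3 schedules the looks by accrual: "Interim analyses will be conducted after enrollment of approximately: 25%, 50%, 75%, and 100% of participants are enrolled". On the boundary it says "A Lan-DeMets spending function analog of the O'Brien-Fleming boundaries will be used for the outcome of" COVID-19-free survival. Its table sets one Z against each sample size: 3.1 at about 875, 3.1 at about 1750, 2.78 at about 2625, and 2.30 in the Final row at 3500. The P-value column reads .0019, .0036, .0179 and .025. The text adds "The provided table assumes four interim analyses with the final analysis with an overall alpha=0.025", although the table has three interim rows and a Final row. It also says "The boundaries are truncated at |Z| = 3.01", while the table uses 3.1.

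Section 10.4 defines the primary test: "We will compare survival in a time-to-event analysis for COVID-19-free survival using Log-rank test". Section 4.1 says "This is an event-driven trial. Subjects will be followed until study termination". Section 4.3.5 places the last outcome assessment at the common closing date: "Study termination virtual visit (to be completed on or shortly after the common closing date for the study". The Summary (Duration of Participation) says "Recruitment is expected to take 4 weeks, for a total study duration of 8 weeks", and adds that duration will depend on how fast enrolment goes.

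Two decisions are tied to the middle look. Section 10.3 asks the DSMB to consider stopping if conditional power is below 20% with about half enrolled. Section 10.2 re-estimates the sample size from the control-group rate at the second DSMB review.

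**The concern.** For a log-rank test, information accrues with events, not with enrolment. When recruitment is quick and follow-up continues afterwards, most events come late, so half enrolled is far from half the information. Boundaries computed for 25/50/75/100% information do not keep their error rate if applied at much smaller fractions, because the test statistics are then less correlated than the table assumes. The 0.025 is already the correction for two doses against one placebo group, so any excess passes straight into the trial's false-positive risk.

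The plan also leaves unclear when 2.30 is applied: at 100% enrolled, at the closing date, or both. Separately, a look with very few events cannot support a sample-size decision, and a conditional-power rule applied there depends heavily on a convention the plan does not state.

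**Working it through.** **1. Reproduce the table.** The two-sided O'Brien-Fleming-type spending function at alpha 0.025 is 4[1 − Φ(2.498/√t)], where 2.498 is the normal quantile at 1 − 0.025/4. At t = 0.75 it gives 4[1 − Φ(2.884)] = 0.0079. At t = 0.25 and 0.50 it gives almost nothing (0.000001 and 0.0008), so the 3.1 cap sets those boundaries. Recursive numerical integration at t = 0.25/0.50/0.75/1 gives Z = 3.10, 3.10, 2.785 and 2.297. The printed Z values spend a cumulative 0.0019, 0.0036, 0.0079 and 0.0248. This matches the table, P-value column included, except row 3 (.0179 printed, .0079 computed). The table therefore treats percent enrolled as percent of information.

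**2. Event fractions at the enrolment looks.** Inputs from the documents: 1165 per group, 10% placebo risk and HR 0.65 (10.2); 4 weeks of recruitment and 8 in total (Summary). Assumptions: uniform accrual over A weeks, constant hazard λ, 10% mean risk reached at close, no loss. The fraction of events at week s ≤ A is [s − (1 − e^(−λs))/λ] / (0.10A). For 4+4 weeks (recruitment + further follow-up), λ = 0.0176 per week. At s = 2 (half enrolled): (2 − 1.9652)/0.4 = 0.087, or 1165 × 0.10 × 0.087 ≈ 10 placebo events. With the loss rates of 10.2 included, the fraction stays at 8.7 to 9.4%.

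**3. Alpha with the printed Z values (3.1 at the first two looks).** Crossing probabilities under the null:

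| Weeks | % of events at the four looks | 2.30 at close | 2.30 only at 100% enrolled | 2.30 at both | Final Z that holds 0.025 at close |
|---|---|---|---|---|---|
| 4+4 | 2/9/19/34 | 0.0292 | 0.0271 | 0.0444 | 2.38 |
| 8+4 | 3/13/29/51 | 0.0287 | 0.0271 | 0.0421 | 2.37 |
| 12+4 | 4/16/35/61 | 0.0284 | 0.0271 | 0.0405 | 2.37 |
| 4+8 | 1/5/12/21 | 0.0295 | 0.0271 | 0.0459 | 2.39 |

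A 4+12 timeline is more extreme still: about 4% of events at half enrolment and alpha about 0.0296 at close. If the last test were at 100% enrolled, power at HR 0.65 would be about 30% on 4+4 (19 to 53% over the four rows).

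**4. Truncation.** With 3.01 instead of 3.1 at the first two looks, alpha is 0.0257 even at true 25/50/75/100% information.

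**5. Re-estimation.** The exact Poisson 95% limits on 10 events are 4.80 and 18.39. Scaling to a cumulative hazard of −ln 0.9 = 0.1054 gives 1 − exp(−0.1054 × 0.480) = 4.9% and 1 − exp(−0.1054 × 1.839) = 17.6%. Over the other three rows, with 6 to 18 placebo events, the interval runs from 4–21% to 6–15%. It always contains both the 8% row of the 10.2 table (N 4353) and the 15% row (N 2334).

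**6. Conditional power below 20%, final Z 2.30, 4+4.** CP = Φ{[Z√t + θ(1 − t) − 2.30]/√(1 − t)}. The design drift is θ = ln(1/0.65) × √(193.6/4) ≈ 3.00, where 193.6 is the expected two-group number of events at close.
- Current trend (θ = Z/√t): the flag is Z < √t[2.30 − 0.8416√(1 − t)] ≈ 0.44. If HR 0.65 is true, its probability is Φ(0.44 − 3.00 × 0.294) ≈ 33% (28 to 36% over the four rows).
- Design effect: the flag needs Z below about −4.2. For an ineffective dose the probability is about 0.001%, and it stays under 1% on every timeline.

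**The case against.** The strongest reply is that 10.3 names a Lan-DeMets function, which exists to accommodate looks at unplanned information times. The table only assumes a schedule, the percentages are approximate, and the DSMB may change the interval. Recomputed at observed events, the boundaries hold 0.025. Even if only the final 2.30 were left unchanged, with the first three looks following the spending function capped at 3.1, alpha would be about 0.0263 on 4+4. That is correct, and it makes the alpha excess conditional on using the table as printed. But 10.3 never names events as the information measure, gives no event counts, and does not say the Z values will be recomputed. A DSMB given this text has only the fixed values to apply.

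Second, 0.029 depends on reading the Final row as the closing-date analysis, whereas the row itself says 100% of 3500. This is fair: the ambiguity is real, and the size of the excess depends on the reading. No reading that uses the printed values gives 0.025.

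Third, the event fractions are scenario outputs, and the futility rule is advisory. Both stand. The percentages in step 6 are therefore flag rates for one comparison, not stopping rates. The mismatch persists on every timeline tried, however, and the re-estimation is not advisory: 10.2 says it will take place.

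Fourth, a stricter final Z costs power: about 2.6 points at 2.38 and about 1 point at 2.33, under step 2's assumptions.

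**Conclusion.** The concern holds. The printed boundaries belong to looks at 25/50/75/100% of events, and 10.3 applies them at 25/50/75/100% enrolled. Used as printed, alpha per comparison is about 0.029 on the best-supported reading (0.028 to 0.030 over the timelines), 0.027 if the last test is at 100% enrolled, and about 0.044 if 2.30 is used both there and at close. The excess on the best-supported reading is modest.

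The half-enrolment look is the larger practical problem. With about 9% of events on 4+4 (4 to 16% over all timelines tried), it cannot distinguish control rates whose required sample sizes differ nearly twofold. Its futility signal is either a frequent false alarm or almost never given, depending on an unstated convention. The figures assume uniform accrual, constant hazard and 10% placebo risk by close. Whether 1165 per group gives 80% power is a separate question on 10.2.

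**What to change.** In Section 10.3:

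1. State the planned number of primary events per comparison at the closing date. Say that each Lan-DeMets boundary is computed from the observed fraction of those events, and replace the fixed Z table.
2. Use one truncation value and recompute the final Z to hold 0.025. On 4+4, with all three interims held at the cap, it is about 2.33 for a cap of 3.1 and 2.36 for 3.01. Uncapped, the boundaries are above 8 at the first two looks, about 5.5 at the third and 2.24 at close.
3. Define the final analysis as the one at the common closing date, and do not spend the final boundary at 100% enrolled. Correct the row 3 P-value.
4. State whether conditional power uses the current trend or the design effect. Set a minimum number of events before the look is acted on: pooled for futility, placebo for re-estimation. Report the interval for the control rate. As examples on 4+4, 20 placebo events arrive at about 70% enrolled (interval about 6 to 15%) and 30 at about 86% (7 to 14%). Waiting for 50% of events would be too late on 4+4: that falls at about week 4.9, after recruitment ends.
5. Reconcile the DSMB trigger in 14.4 (every 450 participants completing 90 days) and the second review in 10.2 with these looks.

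The cost is protocol, SAP and DSMB-charter wording, with no change to planned sample size or data collected. Pooled COVID-19 counts are already in the monthly report of 14.4 but would need reading more often on an 8-week timeline. The downsides are very strict early boundaries if uncapped, the small power loss noted above if capped, and a later re-estimation. Twenty placebo events fall at 53 to 58% enrolled with 8 to 12 weeks of accrual, but at about 91% on 4+8, where 30 arrive only after enrolment closes.

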10.2 Sample Size Considerations

The planned sample size is up to 3500 participants. There will be two comparisons: treatment once weekly compared to placebo, and treatment twice weekly compared to placebo. With 1165 participants in each of the two treatment groups and in one placebo group, a two-sided log-rank test achieves 80% power at alpha = 0.025 significance level to detect a hazard ratio of 0.65 when COVID-19 free survival is 90% in the placebo group.

The study is powered at alpha = 0.025 to account for the two treatment versus placebo comparisons. The two treatment groups will be compared to the same placebo group. Assumed loss to follow-up is 5% in the treatment groups and 15% in the placebo group. With 3500 participants approximately 310 COVID-19 or death events are anticipated.

Sample Size Re-estimation:

At the time of the second DSMB review, a sample size re-estimation will occur based on the disease transmission rate in the control group. The conservative *a priori* assumption (based on limited data) is 10% transmission risk. The table below shows that if the transmission rate is 8% (lower than assumed) then the sample size would need to be increased to a total of 4353 participants. On the other hand, if the transmission rate is greater than the assumed 10% then the sample size can be decreased.

Sample size requirements to detect a hazard ratio of 0.65 based on COVID19 transmission rates without treatment (assuming 80% power, alpha = 0.025, 15% loss to follow-up in the placebo group and 5% loss to follow-up in the treatment groups)

COVID 19 Transmission Rate Without Treatment	Number Per Group	Total Sample Size (3 Groups)
8%	1451	4353
10%	1163	3489
12%	971	2913
15%	778	2334
18%	650	1950
20%	580	1740

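### The P-value column of the interim stopping table does not match its own Z boundaries; used as labelled, it raises type I error per comparison from 0.025 to 0.035

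*Combined protocol and SAP*

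**What the plan says.** Section 10.2 sets the error level for each comparison: "a two-sided log-rank test achieves 80% power at alpha = 0.025 significance level". It also gives the reason: "The study is powered at alpha = 0.025 to account for the two treatment versus placebo comparisons".

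Section 10.3 names the method ("A Lan-DeMets spending function analog of the O'Brien-Fleming boundaries will be used for the outcome of" COVID-19-free survival) and the timing: "Interim analyses will be conducted after enrollment of approximately: 25%, 50%, 75%, and 100% of participants are enrolled". It introduces the boundary table with "The provided table assumes four interim analyses with the final analysis with an overall alpha=0.025. The boundaries are truncated at |Z| = 3.01". The table reads:

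| Look | Enrolled | Z | P-value |
|---|---|---|---|
| 1 | about 875 (25%) | > 3.1 | .0019 |
| 2 | about 1750 (50%) | > 3.1 | .0036 |
| 3 | about 2625 (75%) | > 2.78 | .0179 |
| Final | 3500 (100%) | > 2.30 | .025 |

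Nothing in the section says that the last column is anything other than a p-value, or which of the two columns governs.

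**The concern.** Looks 1 and 2 carry the same Z with two different p-values, which is impossible if the column is what its heading says. The text and the table also give different caps, 3.01 and 3.1.

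These are the thresholds for stopping early for efficacy and for declaring success at the end. The primary test in section 10.4 is a log-rank test, whose result is usually reported as a p-value, so comparing it with a column headed P-value is ordinary use of the table. At look 3, any p between .0054 and .0179 crosses one column and not the other. At the final look the same holds for any p between .0214 and .025. Under section 10.3, early halting for efficacy converts the trial at once to an open-label cohort, which ends the randomized placebo comparison and cannot be undone.

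**Working it through.** **Inputs.** All come from sections 10.2 and 10.3: two-sided testing; overall alpha 0.025 per comparison; Lan-DeMets spending of O'Brien-Fleming type; four looks in total, including the final; and the printed Z and P columns. One assumption is needed: the enrolment fractions 0.25, 0.50, 0.75 and 1.00 serve as information fractions, as the table implies.

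**Step 1. Reproduce the Z column.** Cumulative two-sided spending is α(t) = 2 × 2[1 − Φ(z/√t)], where z is the upper 0.0125/2 normal quantile (0.0125 per tail). This gives 0.000001, 0.0008, 0.0079 and 0.0250 at the four looks. Boundaries were solved by recursive numerical integration of the group-sequential statistic with independent increments. Any boundary above the cap was set to the cap, and the later boundaries were re-solved.

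| Cap | Look 1 | Look 2 | Look 3 | Final |
|---|---|---|---|---|
| none | 4.81 | 3.34 | 2.67 | 2.28 |
| 3.1 | 3.10 | 3.10 | 2.785 | 2.297 |
| 3.01 | 3.01 | 3.01 | 2.862 | 2.305 |
| Printed | 3.1 | 3.1 | 2.78 | 2.30 |

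A cap of 3.1 reproduces the printed column. The 3.01 in the text does not. As a check on the code, the classic four-look O'Brien-Fleming bounds at 0.05 (4.049, 2.863, 2.337, 2.024) returned 0.0500.

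**Step 2. Compare the P column with the Z column.** Nominal two-sided p = 2[1 − Φ(Z)]. Cumulative alpha is the probability under the null of having crossed the printed Z boundaries by that look.

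| Look | Z | Nominal p | Cumulative alpha | Printed P-value |
|---|---|---|---|---|
| 1 | 3.1 | .0019 | .0019 | .0019 |
| 2 | 3.1 | .0019 | .0036 | .0036 |
| 3 | 2.78 | .0054 | .0079 | .0179 |
| Final | 2.30 | .0214 | .0248 | .025 |

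As nominal p-values, rows 2, 3 and 4 are wrong. As cumulative alpha, rows 1, 2 and 4 fit (.025 is the design total), but row 3 is .0100 too high (.0179 − .0079). No single label makes the whole column right. One-sided p-values, the other cap and an overall alpha of 0.05 were also tried, and none reconciles all four rows.

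**Step 3. Apply the P column as labelled.** Inverting Z = Φ⁻¹(1 − p/2) gives 3.105, 2.911, 2.368 and 2.241. Cumulative type I error at those boundaries is 0.0019, 0.0050, 0.0203 and 0.0350. The ratio to design is 0.0350 / 0.025 = 1.40. The look-3 threshold is .0179 / .0054 = 3.3 times too lenient.

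**Step 4. Split the effect by row.** Overall type I error per comparison:

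| Rows where the P column is used | Overall alpha |
|---|---|
| none (Z column throughout) | 0.0248 |
| look 2 only | 0.0257 |
| final only | 0.0282 |
| look 3 only | 0.0317 |
| all three interim looks, final at Z 2.30 | 0.0322 |
| all four | 0.0350 |
| all four, with .0079 in place of .0179 | 0.0298 |

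**Step 5. Family-wise error.** Two comparisons share one placebo group. With equal arms the test statistics have correlation 0.5. Simulation with at least 2,000,000 paths gives 0.046 under the Z column and about 0.064 under the P column, against the 0.05 implied by 2 × 0.025.

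**Step 6. The cap.** With the first two boundaries at 3.01 and the printed 2.78 and 2.30 kept, overall alpha is 0.0257. If the later boundaries are re-solved for 3.01, it stays at 0.025.

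**The case against.** The strongest reply is that the plan defines its boundaries in Z. The truncation sentence is written in |Z|, and only the Z column carries inequality signs. A reader who follows Z gets an overall alpha of 0.0248, so the design controls error. Two signs would tell a statistician that the other column is cumulative alpha: the same Z has two different entries, and the last entry equals the overall alpha. Section 8.5 puts a biostatistician in the DSMB quorum. The 0.035 is also a worst case that needs the P column to be used at every look, and a large part of it comes from the single wrong entry at look 3.

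Most of this stands as a limit on the size of the problem. The inflation is conditional, and the range in step 4 is the fair statement of it. The cap conflict is small: an excess of 0.0007 if the later boundaries are held fixed, and none if they are re-solved.

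It does not remove the error. The plan never says that Z governs or that the column is cumulative, and the look-3 entry is wrong on either reading. Section 10.3 also lets the DSMB alter the stopping rules, but that does not correct the table it starts from. Event fractions may differ from enrolment fractions in this event-driven trial (section 4.1), which would shift the alpha totals. They cannot reconcile p with Z within a row, because that conversion does not depend on information time.

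**Conclusion.** The concern holds. The Z column is a correct capped O'Brien-Fleming-type boundary for two-sided alpha 0.025. The P-value column is mislabelled cumulative alpha with a wrong third entry, and the cap in the text disagrees with the table.

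Used as labelled throughout, the P column gives type I error 0.0350 per comparison (a 40% excess over 0.025) and about 0.064 family-wise. Misreading one row gives 0.0257 to 0.0317. Following Z gives 0.0248 and 0.046. The alpha totals assume that information fractions equal the planned enrolment fractions, and the family-wise figures assume equal arms with correlation 0.5. The row-by-row mismatch between p and Z needs neither assumption. Because the table sets the thresholds for efficacy stopping and final success, it must be corrected.

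**What to change.** In section 10.3:

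- Replace the P-value column with nominal two-sided p-values: .0019, .0019, .0054, .0214.
- If alpha spending is to be shown, add a separate column labelled cumulative alpha spent: .0019, .0036, .0079, .025.
- Give one truncation value in text and table. The printed Z column corresponds to 3.1; if 3.01 was intended, the later boundaries must be re-solved (about 2.86 and 2.30) and both columns recalculated.
- State that the decision rule is the Z boundary, recomputed from the spending function at the information observed at each look.

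The cost is a table and text correction in the protocol. The sample size and the visit schedule do not change.
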